7.7.1 Other concomitant treatment

Medication other than that described above, which is considered necessary for the patient’s safety and well-being, may be given at the discretion of the Investigator and recorded in the appropriate sections of the eCRF.

7.8 Post study access to study treatment

At the end of the study, AstraZeneca will not continue to supply study drug to patients/investigators unless AstraZeneca chooses to extend the study. The Investigator should ensure that the patient receives appropriate standard of care to treat the condition under study.

8. STATISTICAL ANALYSES

8.1 Statistical considerations

All personnel involved with the analysis of the study will remain blinded until database lock and protocol violators identified.

8.2 Sample size estimate

Approximately 110 patients are expected to be randomized 1:1 to the EQW + metformin XR and placebo + metformin XR treatment arms (55 patients per treatment arm). The assumed dropout rate (30%) was based on a similar study (SHOT study; 20%), and increased by 10% as the present study is of longer duration, with a more demanding visit schedule. Therefore, a minimum of 39 patients per treatment arm would provide the necessary statistical power.

With 39 patients per treatment group, there is a 90% power to detect a difference in change in 24-hour mean weighted glucose of 18 mg/dL at Week 4 between exenatide once weekly and placebo, assuming an SD of 24 mg/dL. As the plasma exenatide concentrations are expected to continuously increase and achieve steady-state around Week 7-8, the treatment effect on glycemic control will be increased, therefore, it is expected that 39 patients per treatment group will provide >90% power for the Week 10 treatment comparison. With this sample size, there is approximately 83% power to detect a treatment difference in change in FPG of 30 mg/dL, assuming an SD of 45 mg/dL, and approximately 80% power to detect a difference in change in 24-hour mean weighted glucose of 32 mg/dL between treatments, assuming an SD of 50 mg/dL.

The above power calculation is based on a 2-sided t-test at $\alpha=0.05$. Family-wise Type I error will be controlled at 0.05 for primary and secondary endpoints by applying a sequential testing process. The hierarchical order is defined in Section 8.5.2.

8.3 Definitions of analysis sets

8.3.1 Efficacy analysis sets

The Modified Intent-to-Treat (ITT) population will consist of all randomized patients who received at least one dose of randomized study drug. The Modified ITT population will be used for all efficacy analyses.

The Evaluable population will consist of all Modified ITT patients who completed the study and were in compliance of study procedures. The Evaluable population will be used to perform supportive analyses for primary and secondary endpoints.

8.4 Outcome measures for analyses

8.4.1 Primary endpoint

The primary endpoint for this study is the change in 24-hour mean weighted glucose from baseline (Day -1/1) to Day 6 of Week 10 (Day 69/70) and to Day 6 of Week 4 (Day 27/28).

Note: Day 6 data will consist of data from Day 6 \pm 1 day (Days 5 through 7).

There will also be an average of change in 24-hour mean weighted glucose from baseline to Days 1 to 6 of Week 10 and Week 4 calculated (SD, MAGE, “Distance travel”, “Energy”).

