Prior to leaving the study site at this visit, patients will be scheduled to return to the site prior to 16:00 on Day -1. The day of CGM sensor removing is mandatory on Day -1 of the study. The last day of the lead-in period (Day -1) and the pre-randomization visit will be the same day for patients who qualify for, and are to be randomized into, the double-blind treatment period.

4.1.2.4 Lead-in Visit, Day -1, Visit 5

The purpose of the Day -1 Visit is to remove the CGM device (the CGM device should not remain in place longer than 10 days). Patients are to arrive at their study visit prior to 16:00. Study procedures will be performed as listed in Table 2. The IVRS/IWRS should be notified if the patient is discontinued from the study.

The patient will obtain his or her fingerstick blood glucose level and input it to the CGM sensor as calibration points.

Patients will be instructed to take 3-4 tablets of open-label metformin XR once daily with the evening meal (1500-2000 mg).

In addition, patients should be reminded:

- Of the fasting requirements for the Day 1 visit (no food or drink except water at least 8 hours prior to visit).
- To call the investigative site if the fasting daily glucose on 3 consecutive days is ≥ 270 mg/dL (15 mmol/L).
- To bring lead-in study medication and glucose meter to the next scheduled study visit.

- To abstain from tobacco, nicotine or nicotine replacement, alcohol, and caffeine for 24 hours prior to and during the study visits, which include the 24-hour glucose monitoring period.
- To refrain from strenuous exercise, contact sports, and sunbathing for the 24 hours prior to all study site visits.

Prior to leaving the study site at this visit, patients will be scheduled to return to the site on Day 1.

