Patients will be provided a standardized breakfast following guidelines at the study site. The standardized breakfast meal should account for approximately 35% of the daily calorie intake (~700 kcal). The meal should be consumed in 30 minutes. These meals will remain consistent across the Day -7, 22, and Day 64 visits.

For details on the procedures before and after the breakfast meal, see Section 5.3.1.

Patients will administer their dose of double-blind study medication with time of dose noted on the eCRF if the patient is due for their weekly dose of double-blind study medication.

In addition, patients will be reminded:

- To call the investigative site if the fasting daily glucose on 3 consecutive days is ≥ 270 mg/dL (15 mmol/L).
- That the patient must re-calibrate the CGM system device every 12 hours per manufacturer's instructions.
- To bring study medication and glucose meter to the next scheduled study visit.
- To abstain from tobacco, nicotine or nicotine replacement, alcohol, and caffeine for 24 hours prior to and during the study visits, which include the 24-hour glucose monitoring period.
- The timing and content of meals should remain consistent across the 7-day CGM system monitoring period. See Section 3.8.1 for details.
- To refrain from strenuous exercise, contact sports, and sunbathing for the 24 hours prior to all study site visits.
- To take their open-label metformin XR and their dose of double-blind study medication with time of dose noted on the eCRF if the patient is due for their weekly dose of double-blind study medication.

Prior to the end of this visit, the patient will be scheduled for the next study visit (Day 28 with 26, 27, 28 window), to occur prior to 18:00.

4.2.5 Day 28, Visit 10

Patients are to arrive at their study visit prior to 18:00 (Day 28, Week 4) for removing of the CGM sensor. Study procedures will be performed as listed in Table 2. The IVRS/IWRS should be notified if the patient is discontinued from the study.

Study medication will be dispensed. Patients will take their open-label metformin XR and their dose of double-blind study medication with time of dose noted on the eCRF if the patient is due for their weekly dose of double-blind study medication.

Prior to leaving the study site at the end of visit on Day 28, the patient will be scheduled for a Day 57 visit.

In addition, patients should be reminded:

- Of the fasting requirements for the Day 57 visit (at least 8 hours prior to visit).

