Prior to the end of this visit, the patient will be scheduled to return on Day 64 (Week 10) for the standardized breakfast meal PPGT test, to occur between 06:00-10:00.

4.2.8 Day 64, Visit 13

Patients are to arrive at their study visit on Day 64 between 06:00-10:00. Study procedures will be performed as listed in Table 2.

The IVRS/IWRS should be notified if the patient is discontinued from the study. Patients will remain at the study site for collection of PK and biomarker blood samples according to the sampling described below:

- Perform PK blood sampling prior to the meal (see Section 5.4).
- Collect blood samples for biomarker analysis prior to the meal (see Section 5.7).

Additionally, samples will be taken from patients for FPG, HbA1c, and safety laboratory assessments. See Table 4 for a list of the safety laboratory variables.

Patients will be provided a standardized breakfast following guidelines at the study site. The standardized breakfast meal should account for approximately 35% of the daily calorie intake (~700 kcal). The meal should be consumed in 30 minutes. These meals will remain consistent across the Day -7, 22, and Day 64 visits. For details on the procedures before and after the breakfast meal, see Section 5.3.1.

Patients will take their dose of double-blind study medication with time of dose noted on the eCRF if the patient is due for their weekly dose of double-blind study medication.

In addition, patients will be reminded:

- Of the fasting requirements for the Day 70 visit (at least 8 hours prior to visit).
- To call the investigative site if the fasting daily glucose on 3 consecutive days is ≥ 270 mg/dL (15 mmol/L).
- That the patient must re-calibrate the CGM system device every 12 hours per manufacturer's instructions.

- To bring study medication and glucose meter to the next scheduled study visit.
- To abstain from tobacco, nicotine, or nicotine replacement therapy alcohol, and caffeine for 24 hours prior to and during the study visits, which include the 24-hour glucose monitoring period.
- The timing and content of meals should remain consistent across the 7-day CGM system monitoring period. See Section 3.8.1 for details.
- To refrain from strenuous exercise, contact sports, and sunbathing for the 24 hours prior to all study site visits.

Prior to the end of this visit, the patient will be scheduled for the next study visit (Day 70 with 68, 69, and 70 window), to occur prior to 18:00.

4.2.9 Day 70, Visit 14

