5.1 Efficacy assessments

5.1.1 Primary efficacy assessment

5.1.1.1 Mean weighted glucose

The primary efficacy assessment will be the 24-hour mean weighted glucose which will be estimated by dividing the area under the 24-hour glucose curve (AUC_{0-24}) by 24 hours and will be expressed in mg/dL. Detailed calculation will be defined in the statistical analysis plan (SAP). The glucose measurements used for assessment of the primary endpoint will be analyzed from the CGM data.

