8.5.1 Analysis of the primary variable(s)

The primary endpoint of 24-hour mean weighted glucose will be obtained by a CGM method and calculated as the AUC from the 24-hour glucose profile, divided by 24 hours. Details on AUC computations for partially missing 24-hour glucose profiles will be described in the SAP. The changes in 24-hour mean weighted glucose from baseline (Day -1/1) to Day 5-6 of Week 10 (Day 69/70) and to Day 6 of Week 4 (Day 27/28) will be analyzed using a maximum likelihood-based mixed model repeated measures (MMRM) method. The MMRM model will include change in 24-hour mean weighted glucose as the dependent variable; treatment, HbA1c stratum ($<8.5\%$ vs. $\geq 8.5\%$), baseline 24-hour mean weighted glucose, week of visit, and treatment-by-week interaction as fixed effects, and patient and error as random effects. All post-baseline measurements (including early termination visits) of the 24-hour mean weighted glucose will be included in the analysis with no imputation of missing data other than that inherent in the MMRM model. An unstructured covariance matrix will be used for the MMRM analysis, unless the model does not converge, in which case the covariance matrix will be decided upon model convergence status and the Akaike information criterion. The least squares (LS) means, standard errors of LS means, and 2-sided 95% confidence intervals (CI) for the mean change within each treatment group and the difference between treatment groups will be presented. P-values will be provided for the comparison between treatment groups. Data normality will be evaluated. If the data require logarithm transformation to meet the normality assumption for statistical modeling, the LS mean and the corresponding 95% CI will be calculated at the log scale, and the geometric mean ratio and its corresponding 95% CI will be calculated by taking the anti-log of the corresponding values within each treatment group and for treatment comparisons. The 2 primary endpoints will be tested sequentially (Week 10 comparison will follow by the Week 4 comparison) and the family-wise Type I error will be controlled between primary and secondary endpoints. See description in Section 8.5.2.

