8.5.7 Demographic and baseline characteristics

Demographic and baseline characteristics will be summarized by treatment group as well as for all patients combined. Baseline is defined as the last measurement prior to the first randomized dose of double-blind medication. No statistical test will be carried out for comparison of any baseline measurement between the treatment groups.

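### The primary baseline window Day -1/1 cannot hold a complete 24-hour CGM profile, and the earliest permitted sensor removal days (26 and 68) leave no complete profile in the endpoint window

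*Protocol*

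**What the plan says.** **Endpoint.** Section 8.4.1 takes the "change in 24-hour mean weighted glucose from baseline (Day -1/1) to Day 6 of Week 10 (Day 69/70"), with a second comparison in Week 4 on Day 27/28. A note there widens Day 6 by one day either side, to Days 5 through 7. The Day -1/1 label also appears in the synopsis and in Sections 2.1, 2.2, 8.4.3 and 8.5.1.

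**Measurement.** Section 5.1.1.1: "The glucose measurements used for assessment of the primary endpoint will be analyzed from the CGM data". Section 8.5.1: "calculated as the AUC from the 24-hour glucose profile, divided by 24 hours". The same section makes the baseline value a covariate in the MMRM and leaves the handling of partly missing profiles to the SAP.

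**Lead-in removal.** Section 4.1.2.3: "The day of CGM sensor removing is mandatory on Day -1 of the study". Section 4.1.2.4, for that visit: "Patients are to arrive at their study visit prior to 16:00". Section 5.2.6.2 repeats removal on Day -1, and the next insertion is on Day 21.

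**General baseline rule.** Section 8.5.7: "Baseline is defined as the last measurement prior to the first randomized dose of double-blind medication".

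**On-treatment removal.** At the Day 22 visit (Section 4.2.4) the patient is "scheduled for the next study visit (Day 28 with 26, 27, 28 window), to occur prior to 18:00". At the Day 64 visit (Section 4.2.8) the patient is "scheduled for the next study visit (Day 70 with 68, 69, and 70 window), to occur prior to 18:00". Section 5.2.6.2 instead fixes removal on Days 28 and 70 with no window, and the general note under Table 2 lets treatment-period visits move by 3 days either way.

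**The concern.** The baseline enters the primary analysis twice, as the value subtracted and as a covariate. The interim analysis in Section 8.5.4 adopts the same definition. If the stated window cannot be filled, two analysts can reasonably choose different values: a truncated profile from Day -1, or the complete one that ends on Day -1. A truncated profile omits the evening and overnight hours, so it does not measure the same thing as the 24-hour value it is compared with after treatment.

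After randomization the problem is different. A patient seen on the earliest permitted removal day has followed the scheduling text, yet has no complete 24-hour profile on any day that Section 8.4.1 accepts. This is an avoidable loss of primary outcome data caused by the visit window itself.

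**Working it through.** **Inputs.** Day -1 arrival before 16:00 (Section 4.1.2.4). Removal on Days 26 to 28 and 68 to 70, before 18:00 (Sections 4.2.4 and 4.2.8). Day 1 of Week 10 is Day 64/65 (Section 8.4.2), so Day 4 is 67/68, Day 5 is 68/69, Day 6 is 69/70 and Day 7 is 70/71. Since Day 6 of Week 4 is 27/28, Day 5 of Week 4 is 26/27.

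The clock time at which the primary 24-hour window opens is not stated for these days, so I tried several. Section 5.3.1 starts its 24-hour collection 30 minutes before breakfast on meal-test days. Taking breakfast at 06:00 to 10:00 (assumption, from the meal-visit arrival times) gives starts of 05:30 to 09:30. Removal is put at the latest stated clock time, which favours the plan.

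**Formula.** Hours captured = removal time minus window start, limited to between 0 and 24.

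**Baseline, window Day -1/1, sensor off at 16:00 on Day -1**

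| Window opens on Day -1 | Hours captured |
|---|---|
| 00:00 | 16 − 0 = 16 |
| 05:30 | 16 − 5.5 = 10.5 |
| 09:30 | 16 − 9.5 = 6.5 |
| 16:00 | 0 |

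No start time gives 24 hours. Moving the window back one day adds 24 hours to each line, so Day -2/-1 is complete whenever the window's start hour is no later than the hour of removal.

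**On treatment, sensor off at 18:00 (same result for Week 4 and Week 10)**

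| Removal day | Day 4 | Day 5 | Day 6 | Day 7 |
|---|---|---|---|---|
| 28 or 70 | 24 h | 24 h | 24 h | 0 to 18 h |
| 27 or 69 | 24 h | 24 h | 0 to 18 h | 0 h |
| 26 or 68 | 24 h | 0 to 18 h | 0 h | 0 h |

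The ranges run from an 18:00 start (0 h) to a midnight start (18 h); a breakfast start gives 8.5 to 12.5 h. Removal on Day 27 or 69 is rescued by the one-day tolerance, because Day 5 is complete. Removal on Day 26 or 68 is not: the last complete profile is Day 4, outside Days 5 to 7.

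**The plan's power figure, then the illustration.** Section 8.2 uses 39 per arm, a difference of 18 mg/dL, SD 24 mg/dL and a two-sided t-test at 0.05, and states 90%. The noncentrality is 18 / (24 × √(2/n)).

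- n = 39: 18 / (24 × 0.2265) = 3.31 on 76 df, power 90.5%. The stated 90% reproduces.
- 10% lost (assumption): 39 × 0.9 = 35.1, so n = 35; 18 / (24 × 0.2390) = 3.14 on 68 df, power 87.1%.
- 20% lost (assumption): 39 × 0.8 = 31.2, so n = 31; 18 / (24 × 0.2540) = 2.95 on 60 df, power 82.8%.

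These losses treat the affected patients as contributing nothing, which overstates the effect under the MMRM.

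**The case against.** A reader might infer that the trial has no baseline. The documents do not support that. The sensor is worn from Day -8 to Day -1, a complete Day -2/-1 profile exists, and it meets the rule in Section 8.5.7. It is taken before randomization in the same way in both arms, so the wrong label does not by itself bias the comparison. This stands: the fault lies in the label, and the baseline can be measured.

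A reader might also infer that a patient seen on Day 26 or 68 loses the primary endpoint. That depends on the partial-profile rule, which Section 8.5.1 leaves to the SAP. Section 5.2.6.2 has patients wear the sensor until the 7-day monitoring ends, Sections 4.2.5 and 4.2.9 set the visits on Days 28 and 70, and note l to Table 2 reschedules patients who are not on course for the required number of measures. These points limit the harm. They do not remove the conflict: the scheduling text still offers Days 26 and 68, and a partial-profile rule cannot restore hours that were never measured.

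The tempting large figure is one third of patients lost, with 39 falling to 26 per arm and power to 76%. It needs removals spread evenly over the three allowed days, which nothing in the protocol suggests, since Days 28 and 70 are the scheduled days. It also ignores that the MMRM keeps a patient who has either week, and that the 18 mg/dL figure is for Week 4 while Section 8.2 expects a larger effect at Week 10.

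**Conclusion.** Both date conflicts hold as matters of the protocol's own text. No complete 24-hour CGM profile can exist for Day -1/1, which captures at most 16 hours. Removal on Day 26 or 68 leaves no complete profile within Days 5 to 7, with at most 18 hours of Day 5. Confidence in these two statements is high, because they follow from stated days and clock times whichever start hour is used.

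The effect on power is uncertain. The protocol does not say how many patients would use the earliest removal day; at an assumed 10% the fall is from about 90% to 87%, before any recovery through the MMRM. The sample size calculation itself is sound on this point. The matter should be fixed because it touches the definition of the primary endpoint and is cheap to settle, but it does not make the trial unanalysable.

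**What to change.** 1. Wherever Day -1/1 is given as the CGM baseline (synopsis, Sections 2.1, 2.2, 8.4.1, 8.4.3 and 8.5.1), restate it as the last complete 24-hour CGM profile ending on Day -1, that is Day -2/-1, in line with Section 8.5.7. A mean of the complete lead-in profiles is an optional alternative. It may gain precision, but by an amount that depends on day-to-day and baseline-to-outcome correlations the protocol does not give.
2. Reconcile Sections 4.2.4, 4.2.8 and 5.2.6.2 and the general 3-day visit window under Table 2, so that the sensor is not removed before a complete 24-hour profile within Days 5 to 7 has been recorded. That means removal no earlier than Day 27 or 69, and preferably on Day 28 or 70.
3. Tie the insertion day to the removal day. Insertion on Day 21 with removal on Day 28 is 7 days of wear. If the general window moves insertion to Day 18, removal on Day 28 is already 28 − 18 = 10 days, the protocol's wear limit. The same holds for Days 60 and 70.

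The cost is an amendment to wording and slightly less scheduling slack at two visits. No extra visit or measurement is needed.

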2. STUDY OBJECTIVES

2.1 Primary objective

Primary Objective:	Outcome Measure:
To compare the effect on 24-hour mean weighted glucose after 4 and 10 weeks of treatment of EQW plus metformin with placebo plus metformin, using data obtained by a CGM system	Change in 24-hour mean weighted glucose from baseline (Day -1/1) to Day 6 of Week 10 (Day 69/70) and to Day 6 of Week 4 (Day 27/28)

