2.2 Secondary objectives

Secondary Objectives:	Outcome Measures:
To examine the intra-patient variability of the change in 24-hour mean weighted glucose at the beginning and the end of the dosing cycle (Week 10 of treatment in EQW patients), using data obtained by a CGM system	Change in 24-hour mean weighted glucose between Day 1 of Week 10 (Day 64/65) and Day 6 of Week 10 (Day 69/70) within each EQW-treated patient
To compare the effect on fasting plasma glucose (FPG) and 2-hour PPG after 4 and 10 weeks of dosing of EQW plus metformin with placebo plus metformin	Change from baseline (Day 1) to Day 6 of Week 10 (Day 70) and Day 6 of Week 4 (Day 28) in FPG Change from baseline (Day -1) to Day 6 of Week 10 (Day 69) and Day 6 of Week 4 (Day 27) in 2-hour mean weighted PPG (after the breakfast meal)
To compare the following parameters after 4 and 10 weeks of dosing between the EQW plus metformin and placebo plus metformin treatment groups, using data obtained by a CGM system: the effect on 24-hour mean amplitude of glucose excursion (MAGE) the proportion of time patients who had plasma glucose measurements of: <70 mg/dL ≥70 mg/dL and ≤180 mg/dL or >180 mg/dL	Average of change in 24-hour mean weighted glucose from baseline (Day -1/1) to Days 1 to 6 of Week 10 and Week 4 calculated. (standard deviation [SD], MAGE, “Distance travel”, “Energy”)
To compare the effect on HbA1c levels and 2-hour PPG after 4 and 10 weeks of dosing of EQW plus metformin with placebo plus metformin	Change from baseline (Day -1) to Day 6 of Week 10 (Day 69) and Day 6 of Week 4 (Day 27) in 2-hour mean weighted PPG (after the breakfast meal)

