4.1.2 Lead-in period (Visit 2 to Visit 5)

The medical nutrition and metformin XR lead-in period will be 28 days.

If all inclusion criteria have been met without the presence of any exclusion criteria, the patient may be started on the lead-in period study medication.

During the lead-in period, patients will be instructed to take 3-4 tablets of open-label metformin XR once daily with the evening meal (1500-2000 mg). If a patient is on 1500 mg of metformin XR at screening, they will receive 1500 mg metformin XR during the lead-in period. If a patient is on 2000 mg of metformin XR at screening, they will receive 2000 mg metformin XR during the lead-in period. Patients on 2500 mg or 2550 mg of metformin XR daily (850 mg three times a day) will receive 2000 mg of metformin XR.

Patients will be counseled on medical nutrition by a qualified member of the study staff beginning with the first lead-in visit. At the lead-in visit, the patient's current dietary and exercise behavior will be reviewed. Patients will be instructed on medical nutrition in accordance with the ADA guidelines or locally accepted guidelines. Home glucose meters and supplies will be dispensed to patients and SBGM requirements and procedures will be explained (see Section 5.2.6.1). Daily SBGM will be performed throughout the lead-in period. The medical nutrition plan will be reinforced at visits on Day -28, -7, -1, 1, 15, 22, 28, 57, and 64. Patients will be asked to keep a food diary and to record both meal times and portion size. Patients will be asked to bring the food diary in for review during site visits and will return home with the diary.

The lead-in CGM data will be reviewed for compliance. During the 7-day CGM period required during the lead-in phase of the study a 70% compliance rate is required in order to ensure the patient will be randomized.

4.1.2.1 Lead-In Visit, Day -28, Visit 2

Patients are to arrive at their study visit on Day -28. Study procedures will be performed as listed in [Table 2](#). Patients will be provide with a pharmacy card to receive their metformin XR at this visit.

Patients will be instructed to take 3-4 tablets of open-label metformin XR once daily with the evening meal (1500-2000 mg).

In addition, patients will be reminded:

- To call the investigative site if the fasting daily glucose on 3 consecutive days is ≥ 270 mg/dL (15 mmol/L).
- To bring study medication and glucose meter to the next scheduled study visit.

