5.2.6.2 Continuous glucose monitoring system

The CGM system measures the patient's interstitial glucose level using electrodes that measure an electric signal produced by glucose oxidase reaction. The system records data approximately every 5 minutes. The data will remain blinded to the patient during the recording and will be downloaded into a data file. The CGM system sensor will be inserted subcutaneously at the study site on Day -8, Day 21, and Day 63 at evening time prior to 18:00. Patients will be instructed on use of the glucose meter, the CGM system receiver, and calibration of the CGM system device according to the manufacturer's instructions. Patients will continue to wear the CGM system sensor and perform calibration according to manufacturer's instruction until the conclusion of 7-day glucose monitoring, or the 24-hour glucose monitoring period. The timing and content of meals should remain consistent across the 7-day CGM system monitoring period. See Section 3.8.1 for details on the meals. The CGM sensor will be removed at the study site at Day -1 (Week -1), Day 28 (Week 4), and Day 70 (Week 10).

The 7-day assessment using the CGM will be performed during the lead-in period (Day -8 to Day -1), and during the Treatment Period (Day 21 to Day 28 and Day 63 to Day 70). See [Table 2](#) for additional details on when to insert and remove the device.

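### A week of lead-in CGM is recorded, but baseline 24-hour glucose is the single, incompletely recorded period Day -1/1: precision is lost, though nothing is biased

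*Protocol*

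**What the plan says.** Section 5.2.6.2 sets up the lead-in recording: "The 7-day assessment using the CGM will be performed during the lead-in period (Day -8 to Day -1"). Section 4.1.2 makes it a condition of entry, since "a 70% compliance rate is required in order to ensure the patient will be randomized".

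Section 8.4.1 defines the primary endpoint as "the change in 24-hour mean weighted glucose from baseline (Day -1/1) to Day 6 of Week 10 (Day 69/70"), with the parallel change to Week 4; Section 2.1 agrees. The same section widens the on-treatment Day 6 value to Days 5 through 7 but gives no window for baseline. It then adds a multi-day average: "There will also be an average of change in 24-hour mean weighted glucose from baseline to Days 1 to 6 of Week 10 and Week" (the sentence goes on to Week 4). In Section 2.2 the averaged endpoint is "Average of change in 24-hour mean weighted glucose from baseline (Day -1/1) to Days 1 to 6 of Week 10 and Week 4 calculated", so it too starts from the one period. Section 8.5.7 says in general: "Baseline is defined as the last measurement prior to the first randomized dose of double-blind medication".

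In Section 8.5.1 the baseline enters the MMRM as a covariate; the model lists "baseline 24-hour mean weighted glucose, week of visit, and treatment-by-week interaction as fixed effects".

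Section 4.1.2.4 has the patient arrive before 16:00 on Day -1 to have the sensor removed. Day 1 is a separate visit.

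**The concern.** One free-living day of glucose measures a patient's pre-treatment level with error. As a covariate, a noisy baseline explains less of the follow-up value. The treatment difference then has a wider interval than the collected data allow, and chance imbalance at baseline is only partly corrected. An atypical last day before dosing also passes straight into that patient's change score. The averaged endpoint is the most lopsided, with up to six on-treatment days set against one baseline day.

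The chosen day is also poorly placed. The labels Day 27/28 and Day 69/70 end on the day the sensor is removed. Day -1/1 ends the day after removal, so the last full recorded 24 hours would be Day -2/-1.

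**Working it through.** **1. The plan's own figures (Section 8.2).** Inputs: 39 per arm, difference 18 mg/dL, SD of change 24 mg/dL, two-sided alpha 0.05. The noncentrality is 18 / (24 × √(2/39)) = 3.31 on 76 degrees of freedom, giving power of 90.5% against the stated 90%. The other two figures also reproduce: 30/45 gives 82.8% (stated about 83%) and 32/50 gives 79.7% (stated about 80%).

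**2. Model for the baseline.** Scale the variance of a single-day 24-hour mean to 1. Let r be the reliability of one day (the share of variance that is the patient's true level) and c the correlation between true baseline and true follow-up levels. Let k be the number of baseline days and m the number of follow-up days, with independent day-to-day noise. The residual variance after baseline adjustment is

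V(k) = r + (1 − r)/m − (c·r)² / (r + (1 − r)/k).

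The protocol gives neither r nor c. Assumed ranges: r 0.6 to 0.9, c 0.5 to 0.9. Section 8.4.1 can be read as one follow-up day within Days 5 to 7 (m = 1) or as all three pooled (m = 3), so both are shown. The averaged endpoint has m = 6.

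**3. Mid case, r = 0.8, c = 0.7.** Here (c·r)² = 0.3136. The last term is 0.3136/1 = 0.3136 for k = 1 and 0.3136/0.8333 = 0.3763 for k = 6.

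| Endpoint | r + (1 − r)/m | V(1) | V(6) | Reduction |
|---|---|---|---|---|
| Primary, m = 1 | 1.0000 | 0.6864 | 0.6237 | 9% |
| Primary, m = 3 | 0.8667 | 0.5531 | 0.4903 | 11% |
| Averaged, m = 6 | 0.8333 | 0.5197 | 0.4570 | 12% |

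**4. Over the assumed ranges, k = 6.** The reduction is 2 to 22% for the primary endpoint with m = 1, 2 to 33% with m = 3, and 3 to 39% for the averaged endpoint.

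**5. In terms of power.** Take 24 mg/dL as the SD with a one-day baseline. The mid-case SD becomes 24 × √0.909 = 22.9 (m = 1) or 24 × √0.887 = 22.6 (m = 3). Power at 39 per arm rises from 90.5% to 92.9% or 93.5%. Across the ranges it becomes 91.1 to 97.9%.

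**6. How many days are available.** Seventy percent of seven days is 4.9 days' worth of data, not necessarily in whole days. The meal test may fall on Day -7, -6 or -5 (Section 4.1.2.3). Counting 24-hour periods back from removal on Day -1 and stopping before the meal-test day leaves 5, 4 or 3 periods. In the mid case, k = 5 gives a last term of 0.3136/0.84 = 0.3733 and reductions of 8.7% (m = 1) and 10.8% (m = 3). With k = 3 they are 7.0% and 8.7%, power is 92.4 to 92.8%, and the range over all assumptions is 2 to 25%.

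**The case against.** The strongest reply is that nothing here is wrong. The power statement rests on an unadjusted t-test and holds; baseline adjustment comes on top of it. Randomization keeps the treatment comparison unbiased with either baseline. The averaged endpoint, where the loss is proportionally largest, is outside the testing hierarchy of Section 8.5.2. All of this stands and limits the point to efficiency.

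It could also be said that the detail belongs in the SAP. Sections 5.1.1.1 and 8.5.1 do leave the AUC calculation and partly missing profiles to it. The choice of baseline period is not left open: the protocol names it, and names one that the removal schedule cuts short.

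Three stronger readings are tempting but not supported.

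- **Much larger savings.** A reader might hold the SD of change at 24 mg/dL, assume a daily SD of 16 and a between-patient SD of 25 to 45, and get a 28 to 34% reduction, equivalent to 54 to 59 per arm instead of 39. That leaves 24² − 2 × 16² = 64 for the variance of true change, an SD of 8 mg/dL, and so a true-level correlation of 25/√689 = 0.95 to 45/√2089 = 0.98. Nothing in the protocol supports so high a value.
- **A biased averaged endpoint.** A reader might infer bias because its days include the Day 22 or Day 64 meal test and its baseline does not. That mismatch is common to both arms, so it affects within-arm changes, not the treatment difference.
- **An unused lead-in week.** Section 8.4.3 lists a lead-in versus Week 10 comparison, which Section 8.5.3 handles descriptively. The week is absent only from the primary and averaged baselines.

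Finally, averaging the whole lead-in week for the primary endpoint would put the meal-test day into a baseline whose follow-up, Days 5 to 7, has none. That is a fair objection to the simplest remedy, and the fix allows for it.

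**Conclusion.** The point holds as a loss of efficiency in a stated rule. It is not an error in the sample size, and the treatment difference is not biased. With about six baseline days the adjusted variance for the primary endpoint would fall by about 2 to 33%, most plausibly 9 to 11%. Leaving out the meal-test day gives 3 to 5 days and about 7 to 11% in the mid case. Either way power moves by two or three percentage points. For the averaged endpoint the fall is 3 to 39%, 12% in the mid case.

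Every one of these sizes rests on assumed reliability and correlation, and on independent noise between days. The HbA1c stratum in the MMRM already carries some information on baseline level and is ignored here, so the gain may be smaller. The direction does not depend on the values chosen within the assumed ranges.

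It is worth acting on because the data are already collected and the design has no slack: 55 × 0.70 = 38.5 expected completers per arm against a stated minimum of 39. The Day -1/1 label has to be reconciled with removal on Day -1 in any case.

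**What to change.** Amend Sections 8.4.1, 8.4.2 and 8.5.1, with the matching entries in Section 2 and the synopsis, before unblinding.

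- **Primary endpoint:** define baseline 24-hour mean weighted glucose as the mean of all valid 24-hour lead-in CGM periods after the standardized-meal day, ending at sensor removal on Day -1. Use the same value for the change score and the MMRM covariate.
- **Days 1 to 6 average:** use the matching lead-in days, including the meal-test day.
- **Section 8.5.7:** state that the CGM endpoints are an exception to the last-measurement rule.
- Leave the post-baseline days and the MMRM as they are.

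The cost is a definition change, with no new data, visits or patients, and the between-arm difference keeps its meaning. There are two drawbacks. The number of valid baseline days will vary between patients, so their baselines will differ in precision. Within-arm changes will be measured from a multi-day level instead of the last day before dosing.
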